3. Study Significance: This study will hopefully provide evidence that Doula enhanced care improves the quality of the healthcare process through improved communication and satisfaction for Black birthing people (primary outcome). In addition, we hope to show Doula enhanced care will improve specific disparities for Black birthing people including cesarean delivery, preterm birth, postpartum depression, and breastfeeding rates (our secondary outcomes). If our study is successful in showing these improvements in birth equity, we will submit an NIH (National Institutes of Health) R01 proposal to conduct a large-scale study on Doula enhanced care to improve the quality of health care for all birthing people. Black mothers have increased risk of cesarean delivery, preterm birth, postpartum depression, and lower rates of breast feeding (1). Poor pregnancy outcomes among Black-birthing people are multifactorial. Doula support during pregnancy and childbirth is associated with improved engagement and communication with the healthcare team, increased satisfactions with the birth experience, and decreased maternal stress (2,3). These factors may explain why Doula support has also proven to lower rates of cesarean delivery, preterm birth, postpartum depression and improve breast feeding rates (3,4,5).
4. Literature Review: Several studies suggest doula services help address birth inequities. First, doula services for pregnant people at risk of poor birth outcomes because of low-income or racial diversity may help disrupt influence of social determinants as predisposing factors for health during pregnancy and childbirth. Second, doula supported people have shortened labor and a decreased need for cesarian deliveries and other high-

risk procedures. They also rate childbirth as less difficult and painful than those without support. This can lead to lowering costs of care for pre-term and cesarian sections. Furthermore, doula services may also facilitate a higher rate of breast feeding.

C. Rationale

1. Based on associations between Doula enhanced care and reductions in cesarean delivery and preterm birth, coverage reimbursement for Doula services have proven to be cost-effective (6). However, there are significant socioeconomic, structural, and systemic barriers to Doula access, often preventing the most vulnerable patients from receiving Doula enhanced services.

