2. By better understanding if Doula enhanced care improves communication and quality of maternal care, we can begin to understand how to improve maternal care for Black birthing people. Also, by having Doula enhanced care available, we might reduce the chances of cesarean delivery and preterm birth and increase the likelihood of breastfeeding.

II. Research Plan and Design

A. Study Objectives:

1. The primary objective of the study is to demonstrate improved perceived communication and quality of maternal care among Black birthing people with Doula enhanced care compared to routine pregnancy care at the University of Kansas Health System. This study's primary outcome is to provide evidence that Doula enhanced care improves communication and satisfaction for Black-birthing people by improving the quality of healthcare with the addition of Doula enhancement to the health care team. In addition, the secondary outcome is to show how Doula enhanced care will improve specific disparities between Black birthing people and their White counterparts, including cesarean delivery, preterm birth, postpartum depression, and breastfeeding rates.

B. Study Type and Design:

This study will be an interventional randomized control trial that will have a control group and an experimental group. These groups will be randomly assigned at the patient's enrollment into the study.

C. Sample size, statistical methods, and power calculation

1. Two test Run patients will receive Doula Care from [name]. This will consist of two prenatal visits.
2. Randomization will be 1:1 and will stop after reaching our desired sample size of forty total patients. Forty patients will be enrolled in the study. Twenty patients will receive Doula enhanced care and Twenty patients will receive routine pregnancy care.

D. Subject Criteria (See Vulnerable Populations appendix, if applicable):

1. Inclusion criteria:

- a. Black birthing people receiving prenatal care with planned delivery at University of Kansas Health System between the ages of 16 and 50 years old.
 - i. Parental consent is not required for minors less than 18 years old because this study is directly related to their pregnancy.
- b. A positive social determinants of health screen.

- c. Patients must have an estimated gestational age of at least 14 weeks, but less than 28 weeks (27.6) when enrolled in the study.

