 - d. Patients may have the following fetal anomalies and participate in the study, but these are not requirements for inclusion:
 - i. soft markers (including pyelectasis), intracardiac echogenic foci, mild ventriculomegaly, thickened nuchal fold, absent or hypoplastic nasal bone, isolated echogenic bowel, short long bones and polydactyl.
2. **Exclusion criteria:**
- a. Pregnancy not viable or pregnancy not intrauterine on ultrasound
 - b. Patients who are not willing to be randomized into not receiving doula enhanced
 - c. Patients who do not plan to delivery at the University of Kansas Health System
 - d. Non-Black birthing people.
 - e. Planned cesarean section
 - f. Patients with a known major fetal anomaly
 - g. Non-English speaking
3. Withdrawal/Termination criteria: Patients who transfer care to another facility or attend fewer than two prenatal appointments will be terminated from the study. Patients who wish to withdrawal may at any time.
4. Participants may participate in other studies at the same time.

E. Specific methods and techniques used throughout the study

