5. Data will be linked to subjects with an alphanumerical identifier and will only include pertinent PHI (Protected Health Information) for the study.
6. Data will be stored and protected in RedCap
7. Clinical Research Coordinator may consent patients over the phone and with a link to the Redcap survey. Coordinator may use a physical paper copy of the consent, or an iPad provided by KUMC to link directly to the Redcap Survey.
8. No data sent outside KUMC.

B. Procedures to protect subject confidentiality:

1. Data will be kept securely in research databases, password protected, and de-identified. Participants will be assigned a random alphanumerical study ID to associate survey responses with the data.

C. Quality Assurance / Monitoring

1. Self-assessment will be used to assure the data collected are accurate, consistent, complete, and dependable.
2. No plans to have ongoing third-party monitoring.

V.Data Analysis and Reporting

A. Statistical and Data Analysis:

1. The department of OBGYN statistician will perform all statistical analysis. For the primary and secondary outcomes, t-tests will be used to compare continuous variables and chi-squared tests will be used to compare categorical variables. Risk ratios will be computed using simple logistic regression and 95% confidence intervals will be reported. Qualitative questions will be coded, and common themes will be identified.

B. Outcome:

1. Our primary objective is to demonstrate improved perceived communication and quality of maternal care among Black birthing people with enhanced Doula enhanced care compared to routine pregnancy care at the University of Kansas Health System. We will use quantitative surveys to assess satisfaction and perceived quality of prenatal, labor and delivery and early postpartum care.

C. Study results to participants: Participants will receive a letter with the study results.

D. Publication Plan: If successful in improving pregnancy care with an increase in perceived quality of care and reduction adverse pregnancy outcomes, we will use our results to write a pilot study and submit a poster or abstract for ACOG or SMFM.

VI. Bibliography / References / Literature Cited

Reference:

1. Society for Maternal-Fetal Medicine and National Birth Equity Collaborative infographic, Strategies to Overcome Racism's Impact on Pregnancy Outcomes." Accessed June 16, 2022 at: https://s3.amazonaws.com/cdn.smfm.org/media/2315/Strategies_to_Overcome_Racism_Infographic.pdf.

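### The plan names the risk ratio but a model whose output is an odds ratio, with no conversion step and no rule for an arm without events

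*Combined protocol and SAP*

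**What the plan says.** Section V.A (Statistical and Data Analysis) gives the tests and the effect measure in two sentences. For primary and secondary outcomes, "t-tests will be used to compare continuous variables and chi-squared tests will be used to compare categorical variables". Then: "Risk ratios will be computed using simple logistic regression and 95% confidence intervals will be reported". This is the only statement about an effect measure in the document. Nothing is said about turning a logistic coefficient into a risk ratio, or about empty or sparse cells.

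The outcomes to which a ratio would most naturally apply are the secondary ones. Section II.A lists disparities "including cesarean delivery, preterm birth, postpartum depression, and breastfeeding rates". Section II.C sets the size: "Twenty patients will receive Doula enhanced care and Twenty patients will receive routine pregnancy care". No event rate is given for any outcome. The primary outcome is a survey of satisfaction and perceived quality (section V.B), with no score or responder cut-off defined, so it is unclear whether a ratio would be computed for it.

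**The concern.** The measure and the method do not match. A logistic model with arm as its only predictor estimates the log odds ratio. An analyst who follows the sentence literally, exponentiates the coefficient and copies the printed interval will report an odds ratio under the name of a risk ratio. The two agree only when the outcome is rare.

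With 40 patients the p-values will say little, so the estimates and intervals are what readers will carry away. Section I.B says that success would lead to a proposal for a large follow-on study, and section V plans a poster or abstract and a results letter to participants. An odds ratio read as a risk ratio could mis-size that follow-on study.

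A second, separate gap is that small arms can produce a cell with no events, and the plan has no rule for that case.

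**Working it through.** **Inputs.** From the documents: 20 patients per arm (II.C), the risk ratio as measure and simple logistic regression as model (V.A). The documents state no event rate, risk ratio or odds ratio, so there is no figure of the plan's own to reproduce. Every rate and table below is an assumption chosen to show the range.

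**1. Odds ratio against risk ratio.** With control risk p0 and doula risk p1, RR = p1/p0 and OR = RR × (1 − p0)/(1 − p1). When RR is below 1 the last factor is below 1, and when RR is above 1 it is above 1. The odds ratio is therefore always the further of the two from 1. Example: p0 = 30%, p1 = 15% gives OR = 0.50 × 0.70/0.85 = 0.41.

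| Control risk | OR when RR = 0.50 | OR when RR = 0.75 |
|---|---|---|
| 5% | 0.49 | 0.74 |
| 10% | 0.47 | 0.73 |
| 15% | 0.46 | 0.72 |
| 20% | 0.44 | 0.71 |
| 30% | 0.41 | 0.68 |
| 40% | 0.38 | 0.64 |
| 50% | 0.33 | 0.60 |

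For an outcome of high frequency: 60% to 80% gives RR 1.33 and OR 1.33 × 0.40/0.20 = 2.67; 70% to 90% gives RR 1.29 and OR 3.86.

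**2. The same with intervals at 20 per arm.** For a events among 20 (doula) and c among 20 (routine), SE(log RR) = √(1/a − 1/20 + 1/c − 1/20) and SE(log OR) = √(1/a + 1/(20 − a) + 1/c + 1/(20 − c)). For 16/20 v 12/20 these are 0.214 and 0.722. Limits are the estimate times exp(±1.96 × SE).

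| Doula v routine | Crude RR (95% CI) | OR (95% CI) |
|---|---|---|
| 16/20 v 12/20 | 1.33 (0.88 to 2.03) | 2.67 (0.65 to 10.97) |
| 4/20 v 7/20 | 0.57 (0.20 to 1.65) | 0.46 (0.11 to 1.94) |
| 4/20 v 8/20 | 0.50 (0.18 to 1.40) | 0.38 (0.09 to 1.54) |

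**3. The same model can give the right answer.** A two-arm logistic model is saturated: its predicted risks are the observed proportions. For 4/20 v 8/20 their ratio is 0.20/0.40 = 0.50, exactly the crude risk ratio. The plan does not say that this step will be taken.

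**4. Chance of an arm with no events.** One arm at risk p has none with probability (1 − p)^20. At least one of two arms has none with probability 1 − [1 − (1 − pc)^20] × [1 − (1 − pd)^20], where pc is the control risk and pd the doula risk.

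| Control / doula risk | Control arm empty | Doula arm empty | At least one empty |
|---|---|---|---|
| 10% / 5% | 12% | 36% | 44% |
| 15% / 7.5% | 3.9% | 21% | 24% |
| 20% / 10% | 1.2% | 12% | 13% |
| 30% / 15% | 0.08% | 3.9% | 4% |

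The mirror case, all 20 patients of an arm having the outcome, also breaks the logistic fit. Its chance for one arm is 12% at a 90% rate and 36% at 95%. If terminations leave fewer than 20 analysed per arm, all these chances rise.

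**5. What happens with an empty arm, 0/20 v 3/20.**
- Logistic regression: log OR drifts to about −22 with SE about 18,000, so there is no usable estimate or Wald interval.
- Modified Poisson: log RR about −21 with a robust SE of 0.58, which is misleadingly small. Changing the model alone does not cure the problem.
- Risk ratio from the table: 0, with a score 95% interval of 0 to 1.21. It is undefined if the routine-care arm is the empty one.
- Risk difference: −0.15. The Wilson limits are 0 to 0.161 for 0/20 and 0.052 to 0.360 for 3/20. The Newcombe limits are −0.15 − √(0² + 0.210²) = −0.36 and −0.15 + √(0.161² + 0.098²) = +0.04.

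**The case against.** The strongest reply is that the sentence is loose rather than wrong in effect. It names the risk ratio as the target, and a competent analyst could obtain it from the logistic model's predicted risks, as step 3 shows. That stands as far as it goes: wrong numbers are not certain. But the plan does not describe the step, and the interval that software prints by default is for the odds ratio.

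A reader might also infer that these outcomes are common and that all the reported effects would be badly exaggerated. The documents do not support that. They give no event rate. Section II.D excludes planned cesarean, so even the cesarean rate in this population is unknown. One cited study's title suggests that breastfeeding initiation can be close to universal, but this trial records breastfeeding at the postpartum visit, so the hint is weak. Postpartum depression is screened on the Edinburgh scale with no stated cut-off, so it is not established that a ratio would be computed for all four secondary outcomes.

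Three further limits stand. The two problems mostly fall on different outcomes: where an empty arm is likely, the odds ratio and risk ratio nearly agree, and at 30% risk an arm is empty with probability 0.08%. An empty arm is not a fault of logistic regression alone. And the mislabelling does not manufacture significance: in every table of step 2 both intervals include 1, and the chi-squared test does not depend on which ratio is reported.

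**Conclusion.** Wrong as written, and it should be fixed before analysis. The named model does not directly yield the named measure, no conversion is described, and there is no rule for empty or full cells. That much rests on the text alone.

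The size rests on assumed rates. If the odds ratio is reported as a risk ratio, the distortion is negligible at control risks of about 10-15% or below, moderate at 30-40%, and severe only above about 50%. Breastfeeding is the likeliest candidate for the severe range. The distortion runs away from 1 in both directions, so an unfavourable result would be enlarged as well as a favourable one. The empty-arm problem matters for the rarer outcomes, with a chance between 4% and 44% over the assumed range.

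The point concerns effect estimates for binary outcomes, chiefly secondary ones. A primary survey score compared by t-test is untouched. For a 40-patient study this does not threaten the main comparison, which is why it ranks as a should-fix and no higher.

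**What to change.** Replace the risk-ratio sentence in section V.A with:

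> For each binary outcome the risk ratio and the risk difference (doula minus routine), with 95% confidence intervals, will be computed directly from the 2x2 table. When an arm has no events or all events, the risk difference with a Newcombe or score 95% confidence interval will be the reported measure.

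No logistic coefficient should be labelled a risk ratio. If logistic regression is kept, either derive the risk ratio and its interval from the model's predicted risks, or call the result an odds ratio. Either is valid if stated in advance.

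The cost is one or two sentences and a line of code, with no change to recruitment, data collection or conduct. The downside is presentational: reported ratios will usually look smaller than the odds ratios would have done.

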1. Laboratory tests: No lab tests will be needed for this study. Study Procedures: We plan to use RedCap electronic data collection tool provided by the University of Kansas Health System. A chart review will be performed to obtain maternal demographic information and secondary outcomes including maternal age, gravity/parity, gestational age at delivery, indication for delivery, mode of delivery, neonatal birthweight, presence of maternal comorbidities such as hypertension, preeclampsia, diabetes, fetal growth restriction, and complications of labor including protracted labor, chorioamnionitis, shoulder dystocia, perineal lacerations, and postpartum hemorrhage. Breastfeeding status at time of postpartum visit will also be collected. This information will be recorded in the RedCap data collection tool. A mixed-methods survey, including eight qualitative and four open ended questions, will be administered by the research coordinator at the postpartum follow-up for both groups. Quantitative questions will assess prenatal, labor and delivery, and postpartum perceived quality of care and satisfaction. Questions will aim to evaluate healthcare communication and perceived quality and respectfulness of care. Qualitative questions will provide the opportunity to comment on the aspect of care that improved the quality of care and contributed to the satisfaction of care. Qualitative responses will be coded to identify common themes. Participants randomized to "Routine Pregnancy Care" will continue to receive routine prenatal care at The University of Kansas and routine pregnancy care during the labor and delivery hospitalization. All postpartum patients at the University of Kansas Health System are screened for postpartum depression using the Edinburgh scale on the day of discharge and at 2 weeks following their delivery by a phone call from a nurse. This will be done for both groups per routine protocol at the University of Kansas Health System. All routine care patients will complete the quantitative survey, have a postpartum follow-up appointment with a provider within 2-6 weeks, and their EHR (Electronic Health Record) will be reviewed to assess the study secondary outcomes. Participants randomized to "Doula Enhanced Care"

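### The cesarean comparison takes no account of parity, and with 20 per arm a chance imbalance could shift it by 5 to 9 points under assumed risks (minor)

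*Combined protocol and SAP*

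**What the plan says.** Section V.A covers the primary and secondary outcomes together: "t-tests will be used to compare continuous variables and chi-squared tests will be used to compare categorical variables". It continues: "Risk ratios will be computed using simple logistic regression and 95% confidence intervals will be reported". Simple logistic regression has one predictor, here the arm. No covariate, stratified analysis or sensitivity analysis is named.

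On allocation, II.C.2 says: "Randomization will be 1:1 and will stop after reaching our desired sample size of forty total patients", and then "Twenty patients will receive Doula enhanced care and Twenty patients will receive routine pregnancy care". It mentions neither blocks nor stratification factors.

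Parity is already in the data set. The chart review in II.E.1 is to obtain "maternal demographic information and secondary outcomes including maternal age, gravity/parity, gestational age at delivery", among other items. Cesarean delivery appears in the hypothesis (I.A.2) and among the secondary outcomes (I.B.3 and II.A). The exclusions in II.D.2 include "Planned cesarean section" but set no limit on parity, so nulliparous and parous participants can both enroll.

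**The concern.** Parity at enrollment is fixed before randomization and may be related to the chance of an unplanned cesarean. With 20 per arm and unstratified allocation, the arms can easily differ by several nulliparous participants. If parity does predict cesarean, part of the crude difference in such a trial reflects who was allocated to which arm rather than the doula.

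The practical problem is the lack of a planned response. The baseline table may show an imbalance of four to six patients. An adjustment chosen after seeing it would be open to the charge of selection, and leaving it out would leave the cesarean result hard to read. I.B.3 says that a successful result would support a larger grant proposal, so readers will look at this comparison even though it is secondary.

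**Working it through.** **The plan's own figure.** The only design figure is the sample size: 20 + 20 = 40, which agrees. No effect size, event rate, alpha or power is given, so nothing further can be reproduced.

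**Inputs from the documents.** 20 per arm, 1:1, no stratification (II.C.2); unadjusted analysis (V.A); parity collected (II.E.1).

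**Assumed inputs, absent from the documents.** Share nulliparous π = 35-50%. Cesarean risk 30-40% in nulliparous and 5-10% in parous participants, so a gap of 20-35 points. Gaps of 10 and 0 points are added for contrast. There is no true treatment effect.

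**Step 1: how often parity is imbalanced.** The SD of the difference in share nulliparous is √[2π(1−π)/20], which is 15.1 points at π = 0.35 and 15.8 at π = 0.50, or about 3 patients. A difference of at least 20 points means at least 4 patients. The exact probability from two Binomial(20, π) counts is 24.5%, 25.8% and 26.8% at π = 0.35, 0.40 and 0.50. The average imbalance in those trials is 25.1, 25.4 and 25.6 points.

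**Step 2: how far the crude difference moves.** Shift = imbalance × risk gap. With an average imbalance of about 25 points:
- gap 20: 0.25 × 20 ≈ 5 points
- gap 35: 0.256 × 35 ≈ 9 points
- gap 10: 0.25 × 10 ≈ 2.5 points

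**Step 3: simulation.** 400,000 null trials per scenario, each run at π = 0.35, 0.40 and 0.50. The ranges below are across π.

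| Nulliparous v parous risk | Gap (points) | Mean crude shift when imbalance ≥ 20 points | Variance, Mantel-Haenszel / crude |
|---|---|---|---|
| 30% v 10% | 20 | 5.0-5.1 | 0.954-0.965 |
| 35% v 10% | 25 | 6.2-6.4 | 0.924-0.935 |
| 30% v 5% | 25 | 6.3-6.4 | 0.892-0.918 |
| 40% v 10% | 30 | 7.5-7.7 | 0.891-0.904 |
| 40% v 5% | 35 | 8.8-9.0 | 0.814-0.847 |
| 20% v 10% | 10 | 2.4-2.6 | 1.003-1.008 |
| 20% v 20% | 0 | 0 | 1.027-1.029 |

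The mean shift of the Mantel-Haenszel difference in the same trials was within 0.1 point of zero throughout.

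**Step 4: check of the variance column.** R² = gap² π(1−π)/[p(1−p)], where p is the overall risk. For 35% v 10% and π = 0.40, p = 0.20 and R² = 0.0625 × 0.24/0.16 = 0.094. The second stratum costs a factor of about 1 + 1/36 = 1.028. The net ratio is 0.906 × 1.028 = 0.93, which matches the table.

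**Step 5: scale.** For gaps of 20-35 points the standard error of the crude difference is about 11-14 points, so the shift is about half a standard error (0.4 to 0.7 across the scenarios). The crude difference averages zero over all trials, and the chi-squared test rejects in about 5%.

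**Step 6: interval coverage.** Nominal 95% intervals for the Mantel-Haenszel risk difference cover about 94% with the Sato variance. With the Greenland-Robins variance the same runs give about 91-93%.

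**The case against.** The strongest reply is that nothing here is invalid. Randomization makes the crude difference unbiased on average, its test holds its level, and its standard error already allows for chance imbalance in parity. That stands. A reader might infer that the planned cesarean analysis is biased or inflates false positives, but it does neither. The shift exists only conditionally, in the roughly one trial in four with a large imbalance.

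A second reply is that the documents do not show parity to be strongly prognostic here. That also stands: they give no cesarean rate, parity mix or parity-specific risk. Excluding planned cesareans may make parous participants lower risk, but a prior cesarean followed by planned labor is not excluded. The 5-9 points must therefore be read with its assumptions.

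A third reply is that adjustment is fragile with so few events, about 7-10 cesareans. That is fair for a multivariable logistic model. It has much less force against a two-stratum Mantel-Haenszel risk difference, which needs no model fit and can be computed with empty cells; the cost is the slightly low coverage shown above.

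Finally, a reader might conclude that every outcome should be adjusted for parity. The documents do not support this. Nothing in them links parity to preterm birth, depression, breastfeeding or the survey responses, and they do not define a single survey score to which an adjusted model could be applied.

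**Conclusion.** The point holds for cesarean delivery only, at minor severity. The plan has no stratification and no covariate, so it has no prepared answer to a parity imbalance that has a 24-27% chance of reaching 20 points. Under the assumed risks, the crude difference in such a trial is off by 5-9 points on average; at a 10-point gap, by about 2.5 points. The precision gain is modest: about 4-19% of variance at gaps of 20-35 points, none at 10 points, and a loss of about 3% if parity is irrelevant. Either way, a secondary comparison with a standard error of 11-14 points remains imprecise. The missing sample-size justification is a larger weakness of this plan.

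**What to change.** In V.A, pre-specify for cesarean delivery a Mantel-Haenszel risk difference and risk ratio with 95% confidence intervals, stratified as nulliparous v parous, and report them beside the crude estimate. Name the variance estimator; the Sato variance did better for the risk difference in the check above.

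Define the stratum as parity at enrollment. II.E.1 takes parity from chart review and the timeline places chart abstraction in months 9-12, so a value read after delivery could count the index birth.

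If the allocation list is not yet built, stratify it by the same two groups with permuted blocks, which also keeps the arms close to 20 each. If it is built, leave it and change the analysis only. Do not extend the adjustment to the survey responses or the other binary outcomes on this evidence.

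The cost is a few sentences in V.A and a few lines of code, with no new data. The downsides are about 3% more variance if parity is not prognostic and coverage of about 94% in sparse strata.

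### No single survey score, item or care phase is named as primary and no multiplicity rule is given, so the plan leaves several uncontrolled ways to declare success on the primary objective

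*Combined protocol and SAP*

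**What the plan says.** The primary outcome is worded in three ways.

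- **Communication and satisfaction.** Section II.A.1: "This study's primary outcome is to provide evidence that Doula enhanced care improves communication and satisfaction for Black-birthing people". Section I.B.3 uses the same pair and labels it the primary outcome.
- **Communication and quality of care.** This is the primary objective as worded in II.A.1 and again in V.B.1.
- **Satisfaction and quality over three phases of care.** Section V.B.1: "We will use quantitative surveys to assess satisfaction and perceived quality of prenatal, labor and delivery and early postpartum care".

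The instrument is described in II.E.1: "A mixed-methods survey, including eight qualitative and four open ended questions". The sentences that follow say "Quantitative questions will assess prenatal, labor and delivery, and postpartum perceived quality of care and satisfaction" and "Questions will aim to evaluate healthcare communication and perceived quality and respectfulness of care", which adds respectfulness as a further construct. The timeline in II.E puts survey creation in months 1-2 and enrolment in months 3-9.

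The analysis, in V.A.1, is: "For the primary and secondary outcomes, t-tests will be used to compare continuous variables and chi-squared tests will be used to compare categorical variables". It also promises 95% confidence intervals. No total score, subscale, primary item, primary phase, response scale, significance level, testing order or definition of success is given.

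**The concern.** The trial sets out to demonstrate improvement, and two later steps depend on success: the publication plan (V.D) and the application for a larger study (I.B.3). Yet the documents do not say which comparison decides success. Four constructs (communication, quality, respectfulness, satisfaction), three phases of care and about eight closed items all fall under the primary outcome, and V.A.1 would allow a test on any of them or on a summary of them. If that choice is made after the answers are seen, a chance result on one item could be presented as success on the primary objective, and a reader could not tell it from a result on a variable named in advance.

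**Working it through.** **Inputs from the protocol**
- 40 patients, 1:1, so 20 per arm (II.C.2).
- Three phases of care (II.E.1, V.B.1).
- Eight closed items (II.E.1). The text prints these as qualitative. They are read here as quantitative, because the four open-ended questions are counted separately and the next sentences speak of quantitative questions.

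**Assumptions, since the documents give no figure**
- Two-sided 5% per test, inferred from the 95% intervals.
- Inter-item correlation r from 0.3 to 0.9, equal for all pairs, with roughly normal item scores.
- For power, a true effect of d = 0.5 SD.

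**The plan's own figure.** The total of 40 cannot be reproduced, because no effect size, SD, significance level or power accompanies it. Working backwards with the t-test, 20 per arm gives 80% power at two-sided 5% only for d of about 0.91.

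**False positives if any significant test counts.** For k independent tests the chance of at least one is 1 − 0.95^k:
- 3 tests (one per phase): 1 − 0.95³ = 14.3%
- 8 tests (one per item): 1 − 0.95⁸ = 33.7%

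Items from one survey are correlated, so 33.7% is an upper figure. Simulating eight correlated t-tests with 20 per arm and no true difference gives:

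| r | Any item, either direction | Any item favouring doula care |
|---|---|---|
| 0.3 | about 30% | about 15% |
| 0.5 | about 25% | about 12 to 13% |
| 0.7 | about 19 to 20% | about 10% |
| 0.9 | about 12% | about 6% |
| one test only | 5% | 2.5% |

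The last column is the relevant one for a claim that doula care improves care.

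**Power of one pre-named test.** The mean of eight items has effect size d / √((1 + 7r)/8). Power comes from the noncentral t with 38 df and noncentrality (effect size) × √(20/2). With d = 0.5 on every item:

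| r | √((1 + 7r)/8) | Effect size of the mean | Power of the mean | Power of one pre-named item |
|---|---|---|---|---|
| 0.3 | 0.622 | 0.80 | 70% | 34% |
| 0.5 | 0.750 | 0.67 | 54% | 34% |
| 0.7 | 0.859 | 0.58 | 43% | 34% |
| 0.9 | 0.955 | 0.52 | 36% | 34% |

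**When averaging hurts.** Suppose only 3 of the 8 items shift, each by 0.8 SD (assumed). The mean then shifts by 3 × 0.8 / 8 = 0.3 SD of an item. At r = 0.5 its effect size is 0.3 / 0.75 = 0.40 and its power 23% (32% at r = 0.3, 19% at r = 0.7). A single affected item, if named in advance, would have 69%.

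**The case against.** **Item-by-item testing is not stated.** A reader might infer that V.A.1 commits the trial to testing each item. It does not. The sentence only matches a test to a variable type, and one t-test on a summed score would fit it equally well. This objection stands. The defect is that the choice is left open, not that a wrong choice has been made.

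**The plan does not simply waste power.** A reader might also infer that item-level testing both inflates error and loses power. Those two harms belong to different rules. Counting any significant item as success has about 77% power at d = 0.5 and r = 0.5, more than the 54% of the mean, but it buys this with a false-positive rate of about 25%. The 34% figure belongs to one item named in advance, whose error is the ordinary 5%. The documents support the concern about error under an any-item reading; they do not support a general claim of lost power.

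**It is a small study.** There are 40 patients, no stated significance level, and results are to be written up as a pilot study (V.D). The inflation therefore applies only if p<0.05 on some item is taken as success. But the aim in II.A.1 and V.B.1 is to demonstrate improvement, and both follow-on steps are conditional on success, so that reading is a live one.

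**The survey is still to be written.** That is no fault in itself: the timeline puts survey creation before enrolment, which leaves time to fix the scoring.

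**A mean is not the only remedy.** One item or one phase score named in advance would also hold the error at 5%, and would do better if the effect is concentrated there. This stands too.

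**Conclusion.** The concern holds in this form: the primary outcome is worded inconsistently, no single variable is primary, and nothing limits the number of tests that could count towards it. Under an any-item reading, the chance of a false claim in favour of doula care is about 6% to 15% for correlations from 0.9 to 0.3, against 2.5% for one test. In either direction it is about 12% to 30%, against 5%. These figures rest on eight closed items, two-sided 5% per test and assumed correlations; the documents supply neither of the last two. They describe what the plan allows, not what it says will be done. The case for one named primary variable rests on error control. The gain in power from averaging is a secondary benefit that depends on similar effects across items and almost disappears at a correlation of 0.9.

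**What to change.** Before the first survey is given:

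- Name one primary variable: the mean of the eight closed items, all on a common response scale, reverse-scored where needed, with a stated rule for missing items.
- Compare it once between arms by t-test at two-sided 5%, with the difference in means and its 95% CI.
- Report phase scores and single items as descriptive.
- Use the same primary outcome wording in I.B.3, II.A.1 and V.B.1.
- In II.E.1, correct the description of the eight questions from qualitative to quantitative, if that is what is meant.

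The cost is a scoring rule and a few lines of text, with no added patients, visits or questions. There are two drawbacks. Single items can no longer be claimed as primary successes, and the mean loses power if doula care moves only a few items. If the team expects the effect to sit in one phase of care, it should weigh this now and, if it prefers, name that phase score as primary instead.
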